3.4.2.1 Time to Complete Response

The time from randomization to first observation of CR will be evaluated.

3.4.2.2 Overall Response Rate (ORR)

ORR is defined as having a complete or partial response (CR+PR). The ORR will be estimated at Days 14, 28, and 56 post-randomization.

3.4.2.3 Proportion of Response

The proportion of participants in each aGVHD response category will be described at Days 6, 14, 28 and 56 post-randomization.

3.4.2.4 Non-relapse Mortality (NRM)

Events for NRM are death from any cause other than relapse/progression of the underlying malignancy. Relapse will be considered a competing risk. Time for NRM will be from time of randomization until the earlier of death from a non-relapse cause or relapse (competing risk). NRM will be estimated at Days 90 and 180 post-randomization.

3.4.2.5 Relapse-free Survival (RFS)

Events for RFS are death from any cause or relapse/progression of the underlying malignancy. Time will be calculated from randomization until the earlier of death or relapse/progression of the underlying malignancy. RFS will be estimated at Day 180 post-randomization.

3.4.2.6 GVHD-free Survival

Participants alive, in CR and without cGVHD will be considered a success for this endpoint. GVHD-free survival will be estimated at Days 90 and 180 post-randomization.

3.4.2.7 Chronic GVHD (cGVHD)

cGVHD is defined per NIH Consensus Criteria (see APPENDIX D). Time will be calculated from randomization until the earlier of diagnosis of cGVHD or death from any cause, with death treated as a competing risk. The cumulative incidence of cGVHD at Day 180 post-randomization will be estimated and maximum severity (mild/moderate/severe) will be described.

3.4.2.8 Relapse/Progression of Underlying Malignancy

The cumulative incidence of malignancy relapse/progression will be estimated with death prior to relapse/progression considered a competing risk. The cumulative incidence of relapse/progression at Day 180 post-randomization will be described.

3.4.2.9 Incidence of Infections

All Grade 2-3 infections (as defined by Appendix G) from randomization will be reported by site of disease, date of onset, and severity. Grade 1 CMV infections requiring treatment that occur post-randomization will also be reported. Incidence of infections will be described in participants

from randomization to 90 days post-randomization. The cumulative incidence of treated CMV post-randomization will be described.

3.4.2.10 Incidence of Toxicities

All Grade 3-5 toxicities according to CTCAE v5 occurring from randomization to Day 56 post-randomization will be described.

3.4.2.11 Pharmacokinetics of T-Guard

A population pharmacokinetic model will be developed for T-Guard based on the SPV-T3a- RTA and WT1-RTA levels measured in samples obtained before each infusion and at the following post-infusion timepoints: 4, 5, 6, 8, and 24 hours for the first infusion, 4, 6, and 24 hours for the second and third infusions, and 4, 6, 24 and 48 hours for the fourth infusion. The time points for blood sampling were based on the $t_{1/2}$ and C_{max} values as determined in the previous studies.

The Population PK model will be used to describe the following metrics:

- C_{inf} : Observed and model-predicted concentration at the end of infusion
- CL: Systemic clearance
- AUC: Model-predicted area under the curve from the start of the current infusion until the next infusion or until 48 hours following for the last infusion
- $t_{1/2}$: Model-predicted terminal half-life
- V_c : Volume of the central compartment

Additionally, the impact of various factors on these measures will be evaluated, including age, weight, BSA, BMI, disease status, and ADA.

3.4.2.12 Immunogenicity of T-Guard

ADA responses in the form of human anti-SPV-T3a-RTA and anti-WT1-RTA antibodies will be evaluated with validated bioluminescence assays in serum samples obtained at baseline and at Days 6, 14, 28, 90, and 180 after initiation of treatment in T-Guard treated participants only.

3.5 EXPLORATORY ENDPOINTS

3.5.1.1 Discontinuation of Systemic Steroids

The proportion of participants that is free of systemic steroid therapy at Day 180 post-randomization will be described.

3.5.1.2 Incidence of CMV Reactivation

The proportion of participants requiring new systemic treatment for a CMV PCR level per institutional practice (participants receiving only SoC viral prophylaxis will not be included in this assessment) for CMV-reactivation by Day 180 post-randomization will be described.

3.5.1.3 Incidence of EBV-associated Lymphoproliferative Disorder

The proportions of participants with EBV-associated lymphoproliferative disorder and EBV reactivation requiring therapy with rituximab by Day 180 post-randomization will be described.

3.5.1.4 Evolution of Cell Populations

The evolution and characterization of specific cell populations over the whole 180 day follow-up period will be evaluated in both treatment arms in selected centers. Samples of approximately 50 participants (25 T-Guard, 25 ruxolitinib) will be taken at Day 0, 14, 28, 56 and 180 and either collected in CytoChex preservation tubes, or stored as viably frozen PBMCs, to allow for phenotypic and functional analysis of specific cell subsets, including e.g., FCM and V-beta repertoire analysis. FCM analysis will include the measurement of the following cell populations: Inflammatory Monocytes & Dendritic Cells, Recent Thymic Emigrants, CD4+, CD8+ Naïve & Memory Cells, CD4+ T Regulatory Cells, NK Cells, γδ T Cells, and B cells.

3.5.1.5 GVHD-related Biomarkers

GVHD-related biomarker concentrations including serum Interleukin 1 receptor-like 1 (ST2) and Regenerating Family Member 3 Alpha (REG3α) concentrations and urine 3-Indoxyl Sulfate (3-IS) concentrations at baseline and at Day 6, 14, and 28 post-randomization will be used to estimate the probability of NRM at Day 180 post-assessment for each participant, using the NRM risk model from (Major-Monfried, Renteria et al. 2018). The proportion of participants with high-risk biomarker status (defined as estimated NRM greater than 0.29) will be described at each time point.

3.5.1.6 Patient Reported Outcomes (PROs)

Patient reported outcomes will be assessed using a subset of the PROMIS measures described in APPENDIX E. PROs will be assessed at baseline and Days 28, 90, and 180 post-randomization.

3.5.1.7 Incidence of TMA

Incidence of TMA as defined in the section [2.4.2](#) will be assessed at Day 6, 14, 21, and 28 post-randomization. A blinded review panel will use to review any participants that develop TMA criteria after randomization and treatment.

3.5.1.8 EASIX Score

EASIX score at time of screening will be described.

3.6 ENDPOINT REVIEW PROCESS

Upon completion of participant follow-up, an Endpoint Review Committee (ERC) will conduct an independent review of site-reported data on a key study endpoint, Day 28 aGVHD response, in order to determine the data to be presented in the primary manuscript and final analysis. This Committee will consist of independent members from centers that are not participating on the study in order to remain unbiased. Each participant's data will be reviewed by ERC clinicians. The adjudicated Day 28 aGVHD response data for each participant will be determined by consensus of the reviewers.

Data will be obtained from the relevant eCRFs and source documents and will be provided to reviewers in a blinded manner with respect to treatment assignment, treatment center, and participant identifier. These data will be kept confidential and will not be discussed outside the

Committee or presented in a public forum. The ERC charter will provide further details on the ERC membership and adjudication process.

CHAPTER 4

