19. Patients who have a BMI greater than or equal to 35 kg/m².
20. Patients who are taking sirolimus must have it discontinued prior to starting study treatment.
21. Female patients who are pregnant, breast feeding, or, if sexually active and of childbearing potential, unwilling to use effective birth control from start of treatment until 30 days after the last treatment dose.
22. Male patients who are, if sexually active and with a female partner of childbearing potential, unwilling to use effective birth control from start of treatment until 65 days after the last treatment dose.
23. Patients with any condition that would, in the investigator's judgment, interfere with full participation in the study, including administration of study drug and attending

required study visits; pose a significant risk to the patient; or interfere with interpretation of study data.

24. Patients whose decision to participate might be unduly influenced by perceived expectation of gain or harm by participation, such as patients in detention due to official or legal order.

Interim Analysis:

This trial will include one interim analysis for futility after 23 participants on the T-Guard arm (~46 participants total) become evaluable for the primary endpoint. One interim analysis for efficacy will be performed once 150 participants on combined arms have reached Day 28 and 100 participants on the combined arms have reached Day 180.

Treatment Description:

Participants will be randomized to receive either T-Guard or ruxolitinib. Participants on the T-Guard arm will receive 4 doses of T-Guard treatment, administered intravenously as four 4-hour infusions at least two calendar days apart. Each dose consists of 4 mg/m² Body Surface Area (BSA). Participants on the ruxolitinib arm will receive 10mg orally of ruxolitinib twice daily for a planned minimal period of 56 days.

Accrual Objective:

The target accrual is 246 participants randomized 1:1 between the treatment arms from approximately 75 transplant centers in the US and Europe.

Accrual Period:

Approximately 34 months is expected for accrual.

Study Duration:

Participants will be followed for 180 days after randomization for a total study duration of approximately 40 months.

Safety Monitoring:

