5.1.2 Randomization and Blinding

Participants will be randomized at the time of enrollment in a 1:1 ratio to the treatment arms. Randomization will be stratified by center region (US vs. Europe) and age group (at least 55 years vs. under 55). Stratified treatment assignments will be generated using permuted blocks of random sizes.

As this is an open-label trial, no blinding will be performed.

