5.2 STUDY ANALYSIS SCHEDULE

Figure 5-2 illustrates the study design and the analyses to be conducted during the course of the trial.

[figure not shown]
After accrual of 12 T-Guard participants (~24 participants in combined arms), the study enrollment will be paused to permit the DSMB to perform a comprehensive review of safety data and confirm that the study may continue (see section 5.3.1). Efficacy of T-Guard will not be formally evaluated during this safety review. Upon DSMB approval, the study will continue for full enrollment.

Once 23 T-Guard participants (~46 participants in combined arms) complete follow-up through Day 28, a futility analysis (see section 5.2.1.1) will compare the CR rate in T-Guard participants to a historical therapy CR rate of 20%.

After 150 participants reach Day 28, two separate analyses will be performed to test whether T-Guard's Day 28 CR rate is superior to:

1. Historical therapy (see section 5.2.1.2), to support T-Guard approval from US regulatory authorities (FDA).
2. Ruxolitinib treatment (see section 5.2.2), to support T-Guard approval from European regulatory authorities (EMA). The superiority of the Day 28 CR rate for T-Guard treatment compared to ruxolitinib treatment will be evaluated. The analysis will take place when:
 - a. 150 participants have reached their day 28 assessment and 100 participants have at least 6 months follow-up.
 - b. If efficacy is not found at this analysis, an analysis will follow once all 246 participants have been enrolled and reached their day 28 assessment (see section 5.2.2). This analysis serves as the final analysis of the primary endpoint. The final analysis of other endpoints will be conducted once all 246 participants complete the 180-day follow-up period.

Figure 5-2: BMT CTN 2002 Study Design and Interim Analysis Plan

[figure not shown]

5.2.1 Simon's Two-Stage Design for Demonstrating Superiority of T-Guard to Historical Therapies for Grade III-IV SR-aGVHD

Single arm evaluations of the T-Guard CR rate alone will be performed to demonstrate improvement over a clinically relevant Day 28 CR rate for patients with Grade III-IV SR-aGVHD, as requested by the FDA. This CR rate will serve as the null hypothesis for the Simon's two-stage analysis. This clinically relevant response rate was determined taking the following into account:

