5.2.1.2 Efficacy Analysis Toward FDA Approval (Stage 2)

An analysis of the T-Guard CR rate will be performed toward obtaining FDA approval once 150 participants (75 per arm) complete the Day 28 assessments and 100 participants have completed the Day 180 assessment. This analysis will consider the CR rate specifically in the 75 participants in the T-Guard arm and will compare this to historical therapies using the second stage of the Simon's design (see [Table 5-1](#)). If 23 or more CRs are observed in this set (30.7% or higher), this will provide evidence of superiority of T-Guard in comparison to historical therapies and will support a request for FDA regular approval. Point and interval estimates of the T-Guard CR rate will be provided for this analysis using the minimum variance unbiased estimator and stagewise ordering confidence intervals proposed in Koyama et al. 2008. The additional requirement of 100 participants with 180 days of follow-up will ensure that sufficient data are available for a safety analysis that would be provided with the application for FDA approval.

5.2.2 Efficacy Analysis for Demonstrating Superiority of T-Guard to Ruxolitinib Toward EMA Approval

An interim analysis for efficacy will be conducted once 150 participants (75 per arm) complete the Day 28 assessments and 100 participants have completed the Day 180 assessment. This analysis will compare the Day 28 CR rates between trial arms (T-Guard vs. ruxolitinib) using logistic regression while adjusting for the stratification factors. An error spending approach will be employed to control the overall type I error rate using the O'Brien-Fleming spending function. Operating characteristics for this design are shown in [Table 5-2](#). This analysis in 150 participants will correspond to a one-sided significance level of approximately 0.44% as shown in the table. If superiority is not found at this analysis, a final analysis will follow once all 246 participants have completed the Day 28 assessment, at which the remaining type I error rate will be spent. A finding of efficacy for T-Guard at either this interim or final analysis will be used to support an application for EMA approval.

Table 5-2: Operating Characteristics for Trial Design

Efficacy Analysis	Sample Size	Information Fraction	Efficacy Boundary		Cumulative Type I Error Rate	Cumulative Power Under Alternative
			Difference in CR Rates	Z Statistic		
1	150	61.0%	20.19%	2.6562	0.44%	34.14%

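### Blinded adjudication of Day 28 response is scheduled after follow-up ends, but the futility, FDA, EMA interim and final primary analyses are all triggered on Day 28 data before that

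*Combined protocol and SAP*

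**What the plan says.** **Adjudication.** Section 3.6 says: "Upon completion of participant follow-up, an Endpoint Review Committee (ERC) will conduct an independent review of site-reported data on a key study endpoint". The endpoint is Day 28 acute GVHD response. The stated purpose is "in order to determine the data to be presented in the primary manuscript and final analysis"; no interim look is named. Reviewers are blinded to treatment, center and participant identity, and work from case report forms and source documents. For the rest, "The ERC charter will provide further details on the ERC membership and adjudication process". The charter is not among the documents.

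**Follow-up.** The synopsis says: "Participants will be followed for 180 days after randomization for a total study duration of approximately 40 months".

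**Blinding of treatment.** Section 5.1.2: "As this is an open-label trial, no blinding will be performed".

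**Analyses of Day 28 CR (Section 5.2).**
- Futility: "Once 23 T-Guard participants (~46 participants in combined arms) complete follow-up through Day 28, a futility analysis" is run. It is non-binding (5.2.1.1).
- FDA Stage 2 test and EMA interim: run when "150 participants have reached their day 28 assessment and 100 participants have at least 6 months follow-up".
- Stage 2 rule (5.2.1.2): "If 23 or more CRs are observed in this set (30.7% or higher), this will provide evidence of superiority" over historical therapy.
- Final primary analysis: when all 246 have reached Day 28. Only the other endpoints wait for Day 180.

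Sections 5.2.1.1, 5.2.1.2, 5.2.2 and 5.5 do not mention the ERC. Section 5.2.1 counts the FDA endpoint from T-Guard initiation rather than from randomization; Section 3.6 does not say whether the ERC reviews that version.

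**The concern.** The sponsor has provided for independent, blinded review of this endpoint, but the stated timing puts it after the analyses meant to support the FDA and EMA applications. Part of the CR call is clinical judgment at the site (extent of rash, persistence of nausea or anorexia, the decision to add systemic therapy), made by staff who know the treatment.

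The FDA test matters most. It has no concurrent control, so over-calling common to both arms does not cancel. It is also the last FDA test in the plan, so adjudication after follow-up cannot inform it. For the final primary analysis, Section 3.6 says the ERC determines the data, while Section 5.2 runs that analysis before Section 3.6 lets the ERC begin.

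**Working it through.** **1. Timing.** Accrual takes about 34 months (Section 5.1.1). With 30.4 days per month:
- last Day 28 visit: 34 + 28/30.4 = 34.9 months;
- last Day 180 visit: 34 + 180/30.4 = 39.9 months.

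The final primary analysis can therefore fall due about 5 months before follow-up ends. The 23- and 150-participant analyses come earlier still.

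**2. Kinder reading.** Suppose completion of follow-up means each participant's own Day 180. Futility has no Day 180 requirement, so none of its 23 need be adjudicated. At the 150-participant look only 100 must have reached Day 180, so up to 150 − 100 = 50 could be unadjudicated.

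**3. Reproducing the FDA rule (Table 5-1).** Inputs: n1 = 23, futility at 4 or fewer CRs, n = 75, success at 23 or more.

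P(futility) = P(X1 ≤ 4), with X1 ~ Bin(23, p).

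P(success) = Σ over x = 5 to 23 of P(X1 = x) · P(X2 ≥ 23 − x), with X2 ~ Bin(52, p).

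Futility probabilities at 20%, 26% and 43% come out at 50.1%, 24.8% and 0.9%, as stated. Power at 43% is 98.2% (stated 98%). Type I error at 20% is 1.75%, within the 2.5% limit.

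**4. Sensitivity at the boundary.** Ordinary exact (Clopper-Pearson) 95% lower limits:
- 23/75 (30.7%): 20.5%;
- 22/75 (29.3%): 19.4%.

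The plan will report a stagewise-ordering interval instead, but the decision rule itself turns on the same single CR.

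**5. Effect of an assumed over-call on the FDA test.** The documents give no misclassification rate. Assume a true rate of 20% and a net over-call of d points, so that sites record 20% + d. In 75 participants, 2 points is 0.02 × 75 = 1.5 CRs and 4 points is 3 CRs.

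| Net over-call | Recorded rate | P(futility stop) | P(Stage 2 success) |
|---|---|---|---|
| 0 | 20% | 50.1% | 1.75% |
| 2 points | 22% | 40.7% | 4.8% |
| 3 points | 23% | 36.3% | 7.3% |
| 4 points | 24% | 32.2% | 10.7% |

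**6. Effect on the two-arm interim.** Simulating Table 5-2 with an unpooled difference in proportions and the Stage 1 futility rule gives interim type I error 0.44% and power 34.1%, against stated values of 0.44% and 34.14%.

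The plan's test is logistic, so sensitivity uses the unadjusted Wald statistic on the log odds ratio: Z = [ln(xT/(75 − xT)) − ln(xC/(75 − xC))] / √(1/xT + 1/(75 − xT) + 1/xC + 1/(75 − xC)). It rejects at Z ≥ 2.6562, 75 per arm, by exact enumeration without the futility rule:

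| Recorded T-Guard vs ruxolitinib | P(reject at interim) |
|---|---|
| 26% vs 26% | 0.34% |
| 29% vs 26% (T-Guard-only over-call) | 1.1% |
| 31% vs 26% (T-Guard-only over-call) | 2.1% |
| 29% vs 29%, or 31% vs 31% (equal over-call) | about 0.35% |

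Over-calling therefore matters here only if it differs between arms.

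**The case against.** **Use of site data is inferred.** No section says which response data the looks use, and the unsupplied charter could provide for interim adjudication. This stands. It limits the point to what the protocol's wording implies; that wording still points away from interim adjudication.

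**A reader might infer that the interim and final looks use two different versions of the endpoint.** The documents do not establish this. If the ERC acts only after all follow-up, the final primary analysis at Day 28 of all 246 is unadjudicated too, and both looks share one version. What they show is a conflict between Sections 3.6 and 5.2.

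**A reader might infer that the ERC is the only safeguard against assessment bias.** That is too strong. Bilirubin and stool output are measured criteria (Appendix C). CR also requires survival and no added systemic therapy, and missing assessments count as failures (Section 5.5). A subset of data is checked against source (Section 4.3.1). These narrow the room for over-calling but do not replace blinded review.

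**Earlier adjudication would not remove all bias.** The ERC re-reads what unblinded sites recorded and cannot correct how a rash or symptom was judged at the bedside. This stands, so the tables above are not the gain from the fix.

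**The over-call rates are hypothetical and the direction of any bias is unknown.** This also stands. Futility carries less weight: it is non-binding, and over-calling makes a futility stop less likely without itself producing an efficacy claim.

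**Conclusion.** The point holds as a conflict in timing and a gap in the specification of the registration tests. Taken as written, Section 3.6 puts adjudication after every formal analysis of Day 28 CR in Section 5.2. On the per-participant reading, the 23 at futility and up to 50 of the 150 still lack assured adjudication. Sections 3.6 and 5.2 cannot both be followed as written for the final primary analysis.

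No stated operating characteristic is wrong; the question is which version of CR they apply to. The FDA Stage 2 test is the most exposed, since one reclassified CR at the boundary reverses it. Its inflation, and that of the two-arm interim, depend on the assumed over-calls shown above. They indicate sensitivity and are not evidence that sites over-call.

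**What to change.** Amend Section 3.6 so that the same ERC adjudicates Day 28 response on a rolling basis, covering both the post-randomization version and the post-T-Guard-initiation version used for the FDA test. Table K-1 already arranges post-initiation assessment where T-Guard starts 2 or 3 days after randomization.

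Lock adjudication before the 150- and 246-participant analyses, and preferably before the non-binding futility look. State in Sections 5.2.1, 5.2.2 and 5.5 that each formal test uses the adjudicated response, with site response as a sensitivity analysis. Align the charter, and make the change before the first data cut so that the data source is not chosen after results are known.

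The cost is protocol, SAP and charter wording and a short delay at each cut. No sample size or boundary changes. Adjudication will reduce bias in what unblinded sites recorded but cannot fully remove it.
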